In the secondary analyses, we will use an exact binomial confidence interval to estimate differences between groups in the percent of subjects with PVL pre-operatively and the rate of increase post-operatively. The null hypothesis that treatment does not reduce the frequency of occurrence of PVL pre-operatively and the rate of increase post-operatively will be tested using Fisher's Exact test. The confidence level will be set at 90% and the Type I error at 10%. The PVL data can also be modeled in a more unified approach using mixture models, where the categorical data for patients with no PVL, and the continuous data for patients with evidence of PVL are modeled jointly.⁸⁸ In addition to these analyses, we will describe compliance, both with treatment and with MRI tests, as well as determine loss to follow-up for the 18 month time point. We will secondarily model TMS, VMWM and the Bayley-III Cognitive and Language Scales as a function of treatment, as well as other potential predictors of fetal brain maturation and development including: gestational age, type of CHD, ethnicity, age at surgery, operative management variables, maternal education and socioeconomic status. Presence of 22q11 deletions or other identified genetic anomaly and apo-lipoprotein E (*APOE*) genotype will be included as covariates in the analysis of the Bayley-III scores.

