Table 1 shows that for the Bayley-III Motor Scale, assuming 40 evaluable subjects per treatment group, and an SD of 15, the $\frac{1}{2}$ width of a two-sided 90% confidence interval on the mean difference is expected to be 5.6. Thus, for example, if the mean difference is 6.0 units, a clinically relevant value for this population, the 90% two-sided confidence interval is expected to be on the order of (0.4, 11.6), suggesting that while only a minor effect cannot be ruled out, important positive effects of progesterone appear possible. In contrast, if there is no effect of progesterone we expect an interval centered around zero with i.e. (-5.6, 5.6). This initial study will thus provide important information about the magnitude of the effect of progesterone, and an indication of whether it is worthwhile to proceed with further trials. For TMS, results from [name] (personal communication) estimated the mean (median) value of TMS in a similar cohort to be 10.1 (10.0) with a standard deviation (SD) of 1.06 and range of 8.0 to 13.5. Conservatively assuming an SD that is 25% larger than that in the pilot data (SD=1.32), Table 1 shows that, with a sample size of 60 per group, two-sided 90% confidence intervals for the mean difference in TMS are anticipated to have a $\frac{1}{2}$ width on the order of ± 0.44 . Thus for TMS, if the mean difference is on the order of 2.0, the 90% confidence interval would be (1.56, 2.44). Estimated SD's for VMWM are not yet available.

Table 2: Expected endpoints of 90% confidence interval (CI) for different scenarios for PVL. Calculations are based on Pearson's Chi-square Method for n=60 (pre-surgical) or, conservatively) n=52 (post-surgical) per group.

Proportion in Control Group	Proportion in Treated Group	True Difference in Proportions	Expected Endpoints of 90% CI
Post-natal PVL (pre-surgical, n=60)			
19.0%	8.5%	10.5%	(0.3%, 20.7%)
19.0%	19.0%	0%	(-11.8%, 11.8%)
Post-operative increase in PVL from baseline (n=52)*			
38.0%	24.0%	14%	(-0.8%, 28.8%)
38.0%	38%	0%	(-14.6%, 14.6%) (-15.7%, 15.7%)
*Conservatively as we expect n=52 to 56 post-operatively			

Next we consider the categorical outcomes. In pilot data ([name], personal communication), 19% of subjects had some PVL prior to surgery and 38% of infants increased the level of

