PVL post-surgery. As part of our secondary aims, the pilot study is intended to estimate the differences in these outcomes between groups. To recruit 40 evaluable subjects at 18 months we anticipate having 60 patients available pre-surgery (post-natal) and 52 to 56 after surgery. Table 2 shows that if PVL at baseline is 19% in the control group, and the true effect is 10.5%, then the endpoints of the 90% CI are (0.3%, 20.7%) This would suggest that while we could not rule out essentially a null effect of progesterone, the evidence would suggest a possible substantial effect. In contrast if there were no effect we expect the confidence interval to be centered near zero with endpoints of $\pm 11.8\%$. Similarly, if the post-operative increase in PVL is 38% in the control group, and the true effect size is 14%, then the 90% confidence interval is expected to have endpoints of the 90% CI are (-0.7%, 28.7%). Again, while we could not rule out essentially a null effect of progesterone, the evidence would suggest a possible substantial effect. In contrast if there were no effect we expect the confidence interval to be centered near zero with endpoints of $\pm 15.7\%$.

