5. *Binary Secondary Endpoints* will use an exact binomial confidence interval to estimate differences between groups and will be tested using Fisher's Exact test. The confidence level will be set at 90% and the Type I error at 10%. Binary outcomes include
 - a. Presence of WMI pre- and post-operatively
 - b. Completion of MRIs
 - c. Completion of Bayley III at 18 months
6. *Per Protocol and As Treated*
 - a. The analyses of the primary and secondary endpoints described above will be repeated with alternatives to the intention to treat cohort.
 - b. A 'strict' *per protocol* analysis will be used, considering only those subjects who were eligible for the study and who received the treatment as specified in the protocol. This analysis will consider only those subjects who completed at least 90% of their doses at the time of study-based discontinuation (pre-planned at XX weeks or due to earlier labor and delivery). Adherence will be measured in two ways (1) number of medication doses returned and (2) mother's diaries of medication use. Differences in the two measures of adherence will be described.
 - c. As a sensitivity analysis, a 'relaxed' *per protocol* analysis will follow (a) but use completion of 80% of doses instead of 90% of doses, as the cut-off.
 - d. An *as treated* analysis will consider subjects based on their 'dose of progesterone' based on their assignment to control or intervention arm, as well as adherence to study drug in the progesterone arm. In this case we will include dose as a continuous covariate in a regression model, using linear regression for continuous outcomes or logistic regression for binary outcomes. We will assess interactions between dose and treatment arm. This analysis will estimate the effect of the treatment intervention conditional on different levels of adherence to study medication.

7. *Modeling to Adjust for Covariate Imbalance.* Linear or logistic regression analyses of the primary and secondary outcomes will be carried out with adjustment for baseline covariates of fetal brain maturation and development. The covariates will include type of CHD (primary cardiac diagnosis), race, ethnicity, maternal education and socioeconomic status, presence of 22q11 deletions, other identified genetic anomalies and (*APOE*) genotype.
8. Missing data and truncation by death

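### PVL precision in Table 2 is worked out with a large-sample method, but the planned analysis uses Fisher's exact test and an interval that is not defined for a two-arm difference; naming a two-sample interval and using Boschloo's test would give modest extra power within the same 10% error

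*Protocol*

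**What the plan says.** - **Planning.** Protocol section 6.4, Table 2, gives expected 90% limits for four PVL scenarios. Its caption says: "Calculations are based on Pearson's Chi-square Method", with 60 per group before surgery and 52 per group after it.
- **Analysis, protocol.** Section 6.3.2 says: "we will use an exact binomial confidence interval to estimate differences between groups in the percent of subjects with PVL pre-operatively", and likewise for the post-operative rate of increase. The null hypothesis "will be tested using Fisher's Exact test". Confidence is 90% and Type I error 10%.
- **Analysis, SAP.** Item 5 of the Efficacy Analysis says that binary secondary endpoints "will use an exact binomial confidence interval to estimate differences between groups and will be tested using Fisher's Exact test", at the same levels. The white-matter outcome is listed there as "Presence of WMI pre- and post-operatively".
- **The term itself.** Section 6.3.3 and the SAP's Safety Analysis use *exact binomial* for adverse-event incidence, which is a single proportion.

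Neither document connects the planning method with the analysis method, says which two-sample interval is meant, or states whether the Fisher test is one- or two-sided. No power is given for PVL.

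**The concern.** There are two separate problems.

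First, the interval is not defined. A Clopper-Pearson type of interval bounds one proportion. For a difference of two proportions there are several exact intervals, and they can differ by several points on the same data. Two analysts following SAP item 5 could report different limits for outcomes whose stated purpose is estimation.

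Second, Table 2 describes a different procedure from the one planned. Fisher's test conditions on both margins, so at these sample sizes its real error rate falls well below the nominal 10%. Some power on the white-matter aims (two of the four secondary aims in section 2.2) is given up although another exact test respects the same limit.

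**Working it through.** **Inputs (section 6.4).** Pre-operative: 19.0% v 8.5%, n=60 per arm. Post-operative increase: 38% v 24%, n=52 per arm. The level is 10% and z = 1.645. I take the test as two-sided, which the documents do not state.

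**1. Reproduce Table 2.** Unpooled Wald: d ± 1.645·√[p₁(1−p₁)/n + p₂(1−p₂)/n].

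- Pre-operative: 0.105 ± 1.645·√(0.19·0.81/60 + 0.085·0.915/60) = 0.105 ± 0.1022, i.e. (0.28%, 20.72%). The table prints (0.3%, 20.7%).
- 19% v 19%: ±11.78%. Printed ±11.8%.
- 38% v 24%: 14 ± 14.75, i.e. (−0.75%, 28.75%). The table prints (−0.8%, 28.8%) and the text (−0.7%, 28.7%), a rounding difference.
- 38% v 38%: ±15.66%. Printed ±15.7%. The ±14.6% in the same cell is the n=60 value (14.58%).

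Pooled variance gives (0.16%, 20.84%) and a continuity correction (−1.39%, 22.39%) for the first row; neither matches. Table 2 is therefore unpooled Wald.

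**2. Recompute with a two-sample score interval (Miettinen-Nurminen).** Solve (d−δ)² = 1.645²·[p̃₁(1−p̃₁)/n + p̃₂(1−p̃₂)/n]·2n/(2n−1) for δ, where p̃₁ and p̃₂ are the maximum-likelihood rates subject to p̃₁−p̃₂ = δ. At Table 2's own rates:

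| Scenario | Wald (Table 2) | Score |
|---|---|---|
| 19.0% v 8.5%, n=60 | (0.28, 20.72) | (0.12, 21.29) |
| 19% v 19%, n=60 | ±11.78 | ±12.01 |
| 38% v 24%, n=52 | (−0.75, 28.75) | (−1.00, 28.50) |
| 38% v 38%, n=52 | ±15.66 | ±15.58 |

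The largest movement is 21.29 − 20.72 = 0.57 point.

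**3. Does the choice of interval matter?** At 11/60 v 5/60, whole counts near the pre-operative scenario (60·0.19 = 11.4; 60·0.085 = 5.1):

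- Wald: (−0.1%, 20.1%)
- Score: (−0.3%, 20.7%)
- Exact unconditional on the score statistic (Chan-Zhang): (−0.75%, 20.75%)
- Exact unconditional on the raw difference (Santner-Snell): (−5.75%, 25.25%)

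The last two are both exact, yet their lower limits differ by 5 points.

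**4. Size and power.** For each pair of counts (x₁, x₂), sum Bin(x₁; n, p₁)·Bin(x₂; n, p₂) over the pairs the test rejects. Fisher rejects when its two-sided p ≤ 0.10. Boschloo uses Fisher's p as the statistic and refers it to its largest tail probability over all common rates. Size is evaluated at the control rate.

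| Scenario | Test | Size | Maximum size over all rates | Power |
|---|---|---|---|---|
| Pre-op, n=60 | Fisher | 6.4% | 8.2% | 42.4% |
| Pre-op, n=60 | Boschloo | 8.8% | 9.9% | 48.2% |
| Post-op, n=52 | Fisher | 6.1% | 6.5% | 38.3% |
| Post-op, n=52 | Boschloo | 9.3% | just under 10% | 46.2% |

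Gain: 48.2 − 42.4 = 5.8 points and 46.2 − 38.3 = 7.9 points. In both settings Boschloo rejects every table that Fisher rejects.

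**The case against.** The case for leaving the plan alone is substantial.

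- **Fisher's test is valid and standard**, and both documents name it. A nominal 10% is an upper bound, and Fisher respects it. This stands: the point concerns efficiency and definition, not error control.
- **No documented power figure is wrong.** The sample size rests on the precision of the Bayley-III Motor Scale, and PVL is secondary and estimation-led. This stands, and it limits the weight of the point.
- **A large-sample formula for planning with an exact analysis is common practice**, and Table 2 barely moves under a score interval. This also stands, but it does not tell the analyst which interval to compute.

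Two stronger readings are tempting and are not supported.

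- A reader might infer that the pre-operative example excludes zero only because of the table's method. It does not: at 19.0% v 8.5% the score interval, (0.12%, 21.3%), also excludes zero. At 11/60 v 5/60 both Wald and score cross zero, so the change of sign comes from rounding the counts. Some stricter exact intervals might cross zero at the design rates, but section 6.4 already says of this example that an essentially null effect could not be ruled out.
- A reader might measure Fisher's loss against the uncorrected Pearson test, which shows power of 51.7% and 47.4%. Pearson's size reaches about 12% at some rates, so part of that gap is only a looser error limit. Boschloo is the fair comparator.

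**Conclusion.** The point holds as a modest improvement. The mismatch between Table 2 and the planned analysis is in the current text of both documents, and *exact binomial* does not identify an interval for a two-arm difference. Replacing Fisher with Boschloo adds 5.8 points of power before surgery and 7.9 after it, within the same 10% limit, though power stays below 50% either way. Table 2's limits move by less than 1 point with the score interval, and no sample size or interpretation changes.

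Assumptions:

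- The test is two-sided. Section 6.3.2 words the PVL null directionally; at one-sided 10%, Fisher's power would be 54.7% and 52.6%.
- Pilot rates and sample sizes are as in section 6.4.
- The SAP's white matter injury (WMI) outcome stands in for the protocol's PVL. The post-operative figures apply to Table 2's outcome, an increase in PVL, whereas SAP item 5 lists presence of WMI post-operatively; its rate may differ.

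**What to change.** In protocol section 6.3.2 and SAP Efficacy Analysis item 5:

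1. Replace the *exact binomial* wording with a named 90% two-sample interval for the risk difference, either Miettinen-Nurminen score or exact unconditional based on the score statistic.
2. Replace Fisher's test with Boschloo's exact unconditional test, and state that it is two-sided at 10%.
3. Recompute the four rows of Table 2 with the named interval, and remove the stray ±14.6% entry from the last row.

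If Fisher's test is kept, steps 1 and 3 are still needed.

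The cost is a few lines of text, four recomputed rows and a test that is less familiar to clinical readers. No extra patients or data are required. A change of test should be settled before anyone making it has seen the comparative white-matter results.

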6.5 Interim Analysis

No interim analysis is planned for this Phase II study.

7 STUDY MEDICATION (STUDY DEVICE OR OTHER STUDY INTERVENTION)

7.1 Description

Crinone® (progesterone gel) is a bioadhesive vaginal gel containing micronized progesterone in an emulsion system, which is contained in single use, polypropylene vaginal applicators. The carrier vehicle is an oil-in-water emulsion containing the water swellable, but insoluble polymer, polycarbophil. The progesterone is partially soluble in both the oil and water phase of the vehicle, with the majority of the progesterone existing as a suspension. Physically, Crinone has the appearance of a soft, white to off-white gel.

Replens is a hormone-free vaginal moisturizer. Ingredients include purified water, glycerin, mineral oil, polycarbophil, carbomer homopolymer type B, hydrogenated palm oil, glyceride, sorbic acid, and sodium hydroxide. This product will act as the placebo in this study.

7.1.1 Packaging

Crinone is supplied in a single use, disposable, white polypropylene vaginal applicator with a teal twist-off cap. Each applicator delivers 1.125 grams of Crinone gel containing 90 mg (8% gel) of progesterone in a base containing glycerin, mineral oil, polycarbophil, carbomer 934P, hydrogenated palm oil glyceride, sorbic acid, purified water and may contain sodium hydroxide.

Replens Long-Lasting Moisturizer is supplied in pre-filled, sealed and individually wrapped applicators.

Both Crinone 8% and Replens will be obtained from commercial sources and stored according to package labeling. The investigational pharmacy will dispense the study medications in a blinded fashion by removing any commercial labeling that contains the identity of the product. The study medications will be dispensed as a 30 +/- 15 day supply. Occasionally the timing of prenatal visits to CHOP may require variation in the amount of drug supplied to a mother at one time.

7.1.2 Labeling

Study drug labeling will be in compliance with applicable local and national regulations

7.1.3 Dosing

Crinone 8% is administered vaginally at a dose of 90 mg twice daily. The rounded tip of the applicator is inserted into the vagina. After insertion, the plunger is pushed to release the gel into the vagina. The applicator is removed.

Replens Long-Lasting Moisturizer will also be dosed at one applicator intravaginally twice daily.

7.1.4 Treatment Compliance and Adherence

The Investigational Pharmacy will keep an Investigational Drug Accountability Record for the medication and placebo, which keeps track of study drug that is received, dispensed and returned. Subjects will be asked to maintain a diary documenting each drug application. Compliance with the treatment protocol will be assessed at each visit. The subject diary will be reviewed. Patients will be asked to return all unused medication packages. Unused study drug will be returned to the Investigational Pharmacy to count the remaining drug to assess compliance. Subjects will not be terminated from the study for non-compliance. However the compliance protocol will be considered in secondary analyses to determine if there is any difference in effect between compliers and non-compliers.

7.1.5 Drug Accountability

The Investigational Pharmacy will keep an Investigational Drug Accountability Record for the medication and placebo, which keeps track of anything that is received, dispensed and returned.

8SAFETY MANAGEMENT

8.1 Clinical Adverse Events

Clinical AEs will be monitored throughout the study.

8.2 Adverse Event Reporting

Unanticipated problems related to the research involving risks to subjects or others that occur during the course of this study (including SAEs) will be reported to the IRB in accordance with CHOP IRB SOP 408: Unanticipated Problems Involving Risks to Subjects. AEs that are not serious but that are notable and could involve risks to subjects will be summarized in narrative or other format and submitted to the IRB at the time of continuing review.

8.3 Definition of an Adverse Event

An adverse event is any untoward medical occurrence in a subject who has received an intervention (drug, biologic, or other intervention). The occurrence does not necessarily have to have a causal relationship with the treatment. An AE can therefore be any unfavorable or unintended sign (including an abnormal laboratory finding, for example), symptom, or disease temporally associated with the use of a medicinal product, whether or not considered related to the medicinal product.

All AEs (including SAEs) will be noted in the study records and on the case report form with a full description including the nature, date and time of onset, determination of non-serious versus serious, intensity (mild, moderate, severe), duration, causality, and outcome of the event.

8.4 Definition of a Serious Adverse Event (SAE)

An SAE is any adverse drug experience occurring at any dose that results in any of the following outcomes:

- death,
- a life-threatening event (at risk of death at the time of the event),
- requires inpatient hospitalization or prolongation of existing hospitalization,
- a persistent or significant disability/incapacity, or
- a congenital anomaly/birth defect in the offspring of a subject.

Important medical events that may not result in death, be life-threatening, or require hospitalization may be considered a serious adverse drug event when, based upon appropriate medical judgment, they may jeopardize the subject and may require medical or surgical intervention to prevent one of the outcomes listed in this definition.

A distinction should be drawn between serious and severe AEs. A severe AE is a major event of its type. A severe AE does not necessarily need to be considered serious. For example, nausea which persists for several hours may be considered severe nausea, but would not be an SAE. On the other hand, a stroke that results in only a limited degree of disability may be considered a mild stroke, but would be an SAE.

The Common Terminology Criteria for Adverse Events (CTCAE) Version 4.0 (<http://ctep.cancer.gov>) provides a grading system that is used to categorize the severity of adverse events, as follows:

Grade	Severity	Definition
1	Mild	Asymptomatic or mild symptoms; clinical or diagnostic observations only; intervention not indicated.
2	Moderate	Minimal, local or noninvasive intervention indicated; limiting age-appropriate instrumental activities of daily living (ADL).
3	Severe	Severe or medically significant but not immediately life-threatening; hospitalization or prolongation of hospitalization indicated; disabling; limiting self-care ADL.
4	Life-threatening	Life-threatening consequences; urgent intervention indicated.
5	Death	Death related to AE

A SAE, as defined above, encompasses CTCAE grades 4 and 5, and any Grade 3 event that requires or prolongs hospitalization, or that substantially disrupts the ability of the subject to conduct normal life functions.

Expectedness

The purpose of reporting is to provide new, important information on serious reactions or events previously unobserved or undocumented. Therefore, all AEs will be evaluated as to whether their occurrence was unexpected, using the following definitions:

- **Unexpected:** An unexpected AE or adverse reaction is one for which the nature or severity is not consistent with information in the protocol, consent form, or product brochure. An AE or adverse reaction also may be categorized as unexpected if the event has not previously been observed at the same specificity and/or severity.

•**Expected:** An event is considered expected if it is known to be associated with the study drug(s) and/or the disease state.

Pregnant subjects: The standard definition for SAE will be used (Section 7.4).

However, the following adverse events will not be classified as SAE for the purposes of this study as they are expected events associated with pregnancy and delivery:

- a) Hospitalizations for treatment planned prior to randomization
- b) Hospitalizations for elective treatment of a pre-existing condition
- c) Miscarriage
- d) Preterm labor / suspected preterm labor
- e) Premature rupture of membranes (PROM) / suspected PROM
- f) Preterm delivery
- g) Preterm delivery in maternal interest
- h) Preterm delivery in fetal interest
- i) Hospitalization for pregnancy induced hypertension
- j) Hospitalization for “maternal discomfort”
- k) Hospitalization for “rest”
- l) Hospitalization for “observation” or “monitoring” for which the women are admitted for a period of less than 12 hours.

Newborn subjects: It is important to note at baseline these newborns are medically fragile pediatric patients requiring high-risk neonatal cardiothoracic surgery. This puts them at risk for many expected adverse events and serious adverse events without any additional interventions. In response to a surgical randomized clinical trial (RCT) run by the Pediatric Heart Network at the NIH, a novel adverse event reporting system was developed for this medically fragile population.⁸⁹ The system is based on the concept of the identification of “sentinel” SAEs. For this study, these events will be

- a. death
- b. listing for cardiac transplantation
- c. endocarditis
- d. thromboembolic event
- e. need for surgical or catheter-based intervention
- f. heart block
- g. hemolysis.

The remaining adverse events will be organized in a code list by body system. We have used this system of sentinel SAE reporting with another RCT study Protocol No 10-007750.

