8.4.1 Relationship of SAE to Study Drug

The relationship of each SAE to the study intervention should be characterized using one of the following terms in accordance with CHOP IRB Guidelines: definitely, probably, possibly, unlikely or unrelated.

Type of Unanticipated Problem	Initial Notification (Phone, Email, Fax)	Written Report
Internal (on-site) SAEs Death or Life Threatening	24 hours	Within 2 calendar days
Internal (on-site) SAEs All other SAEs	7 days	Within 7 business days

Unanticipated Problems Related to Research	7 days	Within 7 business days
All other AEs	N/A	Brief Summary of important AEs may be reported at time of continuing review

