9.4 Regulatory and Ethical Considerations

9.4.1 Data and Safety Monitoring Plan

The purpose of this Data and Safety Monitoring Plan is to ensure the safety of research participants and the integrity of the research data.

Safety of Research Participant:

Protection of the rights and welfare of subjects and their families will be maintained during the recruitment, consenting process, and study participation. [name] and his study team have over a 15-year experience in recruiting and enrolling patients for research studies in the Cardiac Center. Subject privacy and confidentiality will be maintained as described in Section 8.3. All research responsibilities delegated by the principal investigator to study team members will be carried out in accordance with the protocol, federal regulations, federal, state and local laws and institutional policies and procedures. The study team has two research nurses, one of which is a Certified Clinical Research Coordinator (CCRC). If any the results of research procedures appear to be important for immediate clinical care, these results will be provided to the Principal Investigator ([name]) of the study who will forward the information to the subject's surgeon, cardiologist and/or primary physician.

The Principal Investigator ([name]) and Co-Investigators (Drs. [name], [name], [name], [name], and [name],) will be responsible for reviewing subject enrollment data, maternal events, and clinical event data as described in Section 7.4 every 2 weeks. [name] is a pediatric cardiothoracic surgeon. [name] is a pediatric neurologist. Drs. [name] and [name] are fetal cardiologists. Drs. [name] and [name] are experts in Maternal-Fetal Medicine. Data will be reviewed for adverse events and actions appropriate to the event will be initiated.

Data Safety Monitoring Board (DSMB):

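### The list of maternal events exempted from SAE status has no severity condition, so a life-threatening admission for pregnancy induced hypertension could be classed as non-serious

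*Protocol*

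**What the plan says.** Protocol 8.4 defines seriousness by outcome: death, threat to life, inpatient or prolonged hospitalization, lasting disability, or congenital anomaly, with a provision for important medical events. It then ties the definition to CTCAE grades: "A SAE, as defined above, encompasses CTCAE grades 4 and 5, and any Grade 3 event that requires or prolongs hospitalization".

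For pregnant subjects the same section begins "The standard definition for SAE will be used (Section 7.4", followed by a sentence starting with 'However', under which twelve listed events "will not be classified as SAE for the purposes of this study as they are expected events associated with pregnancy and delivery". Item i is "Hospitalization for pregnancy induced hypertension". Items j and k are admissions for maternal discomfort and for rest.

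Protocol 8.3 requires every AE to be recorded with "determination of non-serious versus serious, intensity (mild, moderate, severe), duration, causality, and outcome of the event". Protocol 6.3.3 and the SAP's Safety Analysis tabulate AEs by severity and relationship to study drug, and promise a detailed description of SAEs only. Under 8.2, "AEs that are not serious but that are notable and could involve risks to subjects will be summarized in narrative or other format" and sent to the IRB at continuing review. The timetable printed in 8.4.1 gives the row "Internal (on-site) SAEs Death or Life Threatening" a 24-hour initial notice.

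**The concern.** The only reason given for the exemption is that the events are expected in pregnancy. Expectedness and seriousness are separate judgements, and the protocol's own definition of an unexpected event turns on nature or severity. An exemption that ignores severity therefore sits badly with both definitions.

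Two investigators could classify the same woman differently. One could take the opening sentence as controlling and treat the list as waiving only the hospitalization criterion. The other could follow the 'However' sentence as written and record a life-threatening hypertensive admission as non-serious. The second course loses SAE status and the SAE narrative and, in a narrow set of cases, the fastest IRB notice. The trial gives a drug to pregnant women and compares it with placebo, so serious maternal events should be classified by one rule.

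**Working it through.** There is no planned figure to reproduce. The check is of the wording, plus one calculation of reporting times.

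**1. Does any listed item carry a severity condition?** Items a and b depend on whether treatment was planned before randomization or is elective. Item l depends on duration (under 12 hours). Items c to h name obstetric events, and i to k name reasons for admission. None of the twelve mentions severity, threat to life or outcome.

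**2. Does any other text restore SAE status?** I looked through 6.3.3, 8.2 to 8.5 and 9.4.1 of the protocol and the SAP's Safety Analysis. None says that a listed event becomes serious again if it is life-threatening or fatal.

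**3. Which items could realistically be life-threatening admissions?** Item i is the plain case. An admission for discomfort or rest would rarely be life-threatening.

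**4. What is lost and what is kept under the literal reading?**

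| Element | Life-threatening SAE | Exempt event |
|---|---|---|
| AE record with intensity and causality (8.3) | yes | yes |
| AE tables by severity and relationship (6.3.3, SAP) | yes | yes |
| Two-weekly review of maternal events (9.4.1) | yes | yes |
| Detailed description (6.3.3, SAP) | yes | no |
| Relationship rating on the 8.4.1 five-term scale | yes | not required |
| 24-hour IRB notice, if unanticipated and related | yes | no |

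The intensity scale in 8.3 stops at severe, although 8.4 describes the five CTCAE grades. If the case report form follows 8.3, the AE tables would not separate life-threatening events from severe ones.

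**5. Reporting delay.** Section 8.5 requires prompt IRB notice only for SAEs that are unanticipated and related. For such an event, loss of SAE status moves it from the life-threatening row of the 8.4.1 timetable to the row for unanticipated problems related to research.

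- Initial notice: 7 days − 1 day = 6 days later.
- Written report: 7 business days instead of 2 calendar days. Ignoring holidays, 7 business days from an event on Monday to Sunday is 9, 9, 9, 11, 11, 10 and 9 calendar days. The delay is therefore 9 − 2 = 7 days to 11 − 2 = 9 days.

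**6. Related but not life-threatening.** The timetable gives all other SAEs and unanticipated related problems the same limits: 7 days, then 7 business days. The delay is 0 days.

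**The case against.** The strongest reply is that the list waives only the hospitalization criterion. The standard definition is invoked immediately before it, and a separately recorded complication such as stroke, abruption, preeclampsia or death is not on the list and stays an SAE. That reading is reasonable and may be what was intended. It is not what the 'However' sentence says, and a reader should not have to supply the limit.

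The second reply is that little is lost: AEs are recorded with causality, tabulated, and reviewed every two weeks, and gestational hypertension and preeclampsia are SAP endpoints. This stands, and it keeps the point small.

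A reader might infer more than the text supports in three ways.

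- *The exemption hides drug-related admissions.* Relatedness is not part of the seriousness definition in 8.4. Step 6 shows no change in deadline for a related event that is not life-threatening, and an expected related event needs no prompt notice under 8.5 even as an SAE. Local irritation is the gel's named common effect. That an admission for it would be filed as maternal discomfort is conjecture, and if recorded as irritation it stays an SAE. Neither document names hypertension as an effect of the gel.
- *Only items i to k are defective.* No item has a severity condition, so the correction should cover the whole list.
- *The pointer to Section 7.4 leaves the definition uncertain.* Section 7 has no 7.4. Section 9.4.1 repeats the number ("reviewing subject enrollment data, maternal events, and clinical event data as described in Section 7.4 every 2 weeks") and also cites 8.3 for confidentiality, which is 9.3. The references lag by one section. Correcting them is clerical and favours neither reading.

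**Conclusion.** The wording defect is real and the consequence is small. Read literally, 8.4 lets a life-threatening admission for pregnancy induced hypertension be classed as non-serious, contrary to its own definition. The loss is SAE status, the detailed description and the 8.4.1 rating. For an event that is also unanticipated and related, initial notice comes 6 days later and the written report 7 to 9 days later. No efficacy result and no planned AE interval changes, because exempt events remain AEs.

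This rests on three assumptions. The event is recorded only under the exempt label. It is then reported under the unanticipated-problem row, which is open to it because the protocol's definition of unexpected allows for unusual severity. The AE and SAE reporting lines under the MRI stopping rule in 9.4.2 are taken to apply to the MRI procedures and are not counted either way.

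The number of such admissions cannot be estimated from the documents. The text under the DSMB heading in 9.4.1 was not available, so reporting to the DSMB is not judged. It is a cheap improvement worth making, not a threat to the trial.

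**What to change.** Add after item l in protocol 8.4:

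> *Exemptions a to l waive only the hospitalization criterion; any listed event that is fatal, life-threatening (CTCAE grade 4-5) or results in persistent or significant disability remains an SAE.*

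State that fatal and life-threatening refer here to the woman, since item c (miscarriage) would otherwise always be caught. The sentence leaves a Grade 3 hypertensive admission exempt if hospitalization is the only ground for seriousness, which appears to be what item i was meant to do.

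In the SAP's Safety Analysis, tabulate the exempted maternal admissions by arm, with recorded causality, beside the SAE listing. As a clerical matter, change 7.4 to 8.4 in protocol 8.4 and 9.4.1.

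The cost is one sentence, one table and a few more SAE reports. The SAP is dated March 2022 and describes accrual in the past tense, so the gain in prompt reporting may be limited for this trial. The table can still be produced from the AE records.
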